## **Study Timeline**

### *Baseline:*

Participants who meet inclusion and exclusion criteria will be enrolled into the study after consenting to and before receiving treatment. The baseline examination and all baseline questionnaires will be completed within 8 weeks before the index study treatment procedure (facet joint steroid injection or medial branch radiofrequency ablation) as time is needed to obtain insurance authorization for all study procedures in the present study (all procedures in this

study represent usual care procedures: medial branch blocks, facet joint injections, and medial branch radiofrequency ablation).

*Follow-up:*

Routine scheduled follow-up will occur at 1 month (+/- 2 weeks), 3 months (+/- 4 weeks), 6 months (+/- 6 weeks), 12 months (+/- 3 months), and 24 months (+/- 3 months), at which times all follow-up measures will be obtained.

The 3-month follow-up will serve as the time point for the primary outcome analysis of the randomized trial and an intention-to-treat analysis will be used to evaluate for differences in outcomes between the two groups. The 3-month time point provides a reasonable timeframe to evaluate the clinical effects of the lumbar MBN C-RFA while also providing a humane timeframe for crossover to active treatment in those randomized to usual treatment. All subsequent follow-up periods are intended to evaluate long-term clinical outcomes of lumbar MBN C-RFA and will be evaluated with an as-treated analysis.

The study start date and the outcome assessment timeline will begin at the date of the participant's initial facet-targeted treatment. After 3 months, patients who have failed treatment (not meeting criteria for success, as described above) can be offered alternative treatment. Those who cross-over will be considered treatment failures of the original treatment, by definition, and continue on the regular follow-up schedule. A new 2-year follow-up period will begin upon cross-over.

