This study is intended to monitor outcomes for 2 years following facet joint intervention. Some patients reporting relief at the 3-month follow-up may experience a return of symptoms afterwards. All patients reporting relief at the 3-month follow-up will be instructed to contact their physician if and when they experience a treatment effect that diminishes by >50%. This can occur at any time following the 3-month follow-up, including the regularly scheduled follow-up intervals. Repeating the facet intervention procedure originally assigned beyond the 3-month follow-up does not reset the follow-up schedule. Patients are also free to choose alternative therapies beyond 3 months. Patients may also develop new low back pain that is different from what is being evaluated, which will be noted.

[figure not shown]

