#### *FJI Procedure (Procedure as performed as standard of care clinical practice)*

During the C-RFA procedure, the participant will be positioned prone on a fluoroscopy table. Sterile precautions, including sterile preparation, drapes, and gloves, will be undertaken.

Using an oblique fluoroscopic view, the image intensifier will be rotated to optimize the posterior joint space opening. A spinal needle will be advanced under fluoroscopic guidance to enter the posterior joint space. The needle position will be confirmed in both AP and oblique views. Approximately 0.2-1 mL of iodinated contrast medium will be injected to confirm intra-articular placement and no vascular uptake. The injection will be then completed with 0.5 mL of 40mg/mL Kenalog and 0.5 mL of 1-4% preservative-free lidocaine. This technique will be repeated for each facet joint injected.

For bilateral low back pain, a maximum of 4 facet joints (two on each side) will be injected. For unilateral low back pain, up to 3 facet joints will be injected.

*Group Assignments:*

Patients will be randomly assigned to the two treatment groups (C-RFA vs. FJI) at a 1:1 ratio. Participants who reported 50% or more relief of their usual pain (NPRS score compared to baseline) at the 3-month follow-up time point and who subsequently experience a treatment effect that diminishes by > 50% will be offered a repeat procedure. Duration of relief will be considered the time from the provision of the treatment procedure until the participant returns to 50% of their pre-treatment level of pain as reported during scheduled follow-up, or when a repeat treatment procedure is requested and performed.

*Crossover:*

Any time after the 3-month follow-up, any participant who has not obtained adequate pain relief can ask to cross over to alternative treatment group. In doing so, a new 2-year follow-up will begin for this participant who is now placed in the alternative treatment group for the long-term, as-treated outcomes analysis.

*Co-interventions:*

Patients are allowed to receive usual care, including co-interventions, as deemed necessary by the treating physician. Treatments related to the participant's spine condition will be reported on the ancillary treatment log.

*Primary Outcomes:*

The primary outcome for the randomized trial is the proportion of responders, defined by a reduction in NPRS score  $\geq 50\%$  at the 3-month follow-up.

*Secondary Outcomes:*

1. Physical function (ODI and PF CAT)

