### **Data Analysis**

Results of the randomized comparative trial will be determined by an analysis of categorical data from the 3-month follow-up. At 3-month follow-up, prior to allowing crossover, overall treatment response rates (in the previously defined categories of failure or success) will be calculated for both treatment groups using an intention-to-treat analysis. For time periods beyond 3 months, intention-to-treat and as-treated analyses will be performed with primary reporting based on the as-treated analysis to assess the long-term effectiveness of each treatment. In the intention-to-treat analysis, participants who cross-over will be treated as treatment failures of their original group assignment. In addition, a treatment benefit survival analysis will be performed.

Subgroup analyses will be performed to assess treatment response and long-term effectiveness in patients reporting 100% relief from lumbar MBN blocks as compared with those reporting between 80% relief. Data will also be examined to identify any factors that predict treatment success and need for repeat treatment.

Secondary outcomes will be similarly evaluated. For the assessment of function and global quality of life, the proportions of those achieving and not achieving the established minimal clinically important differences (MCID) will be determined and compared between the two treatment groups at the 6-month follow-up. For long-term analysis of treatment effectiveness, an as-treated analysis will determine the proportion of participants exceeding these response thresholds. In addition to these categorical outcomes, changes in group mean scores will be measured and compared.

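### Two different crossover criteria, combined with scoring every crossover as a failure, let a participant who still meets the success definition count as a failure in the post-3-month ITT analysis

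*Combined protocol and SAP*

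**What the plan says.** Three places describe who may change treatment.

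- Study Timeline, Follow-up: "After 3 months, patients who have failed treatment (not meeting criteria for success, as described above) can be offered alternative treatment".
- The same section, later: "Patients are also free to choose alternative therapies beyond 3 months". No condition is attached.
- Study Protocol, Crossover: at any point once the 3-month visit has passed, "any participant who has not obtained adequate pain relief can ask to cross over to alternative treatment group". Adequate is not defined there or elsewhere, and it is not tied to the 50% NPRS threshold.

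Two places say how a crossover is scored.

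- Study Timeline, Follow-up: "Those who cross-over will be considered treatment failures of the original treatment, by definition, and continue on the regular follow-up schedule".
- Data Analysis: "In the intention-to-treat analysis, participants who cross-over will be treated as treatment failures of their original group assignment". No NPRS value is consulted.

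Primary Outcomes defines a responder as a participant with an NPRS reduction of at least 50% at 3 months. Data Analysis calculates the 3-month ITT response rates before crossover is allowed. For later times it plans both ITT and as-treated analyses and makes as-treated the primary report.

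**The concern.** Calling a crossover a failure by definition is sound only if failure is the entry condition for crossing over. The Follow-up text makes it so; the Crossover paragraph does not. Under the latter, a participant can satisfy the 50% threshold, judge the relief inadequate, switch, and be scored as a failure of the assigned treatment.

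Such a participant is easy to picture. Entry requires an NPRS of 5/10 or more. Someone who falls from 10 to 5 is a responder, yet still has pain at the entry threshold.

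At stake are the ITT response rates at 6, 12 and 24 months, which can move with no change in any pain score. The plan accepts that participants cannot be blinded, so requests could differ by arm for reasons other than pain. The as-treated analysis does not escape the ambiguity either: a crossover is placed in the other group with a new 2-year follow-up, so the same undefined criterion decides who moves between as-treated groups.

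**Working it through.** **1. The two criteria applied to the same participant**

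The last two rows assume that the 50% threshold is carried forward to later visits. The plan states the responder definition for 3 months only.

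| Participant after 3 months | Eligible under Follow-up text | Eligible under Crossover paragraph | ITT score if crossed over |
|---|---|---|---|
| Reduction below 50%, relief judged inadequate | Yes | Yes | Failure; agrees with the threshold |
| Reduction 50% or more, relief judged inadequate | No | Yes | Failure; disagrees with the threshold |
| Reduction 50% or more, relief judged adequate | No | No | Does not arise |

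The conflict sits in the second row.

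**2. The plan's own figure**

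Power Analysis gives 80% vs 50%, alpha 0.05, power 0.80, and 39 per group; Statistical Analysis specifies two-tailed tests. With a pooled variance and no continuity correction:

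n = [1.960 × √(2 × 0.65 × 0.35) + 0.842 × √(0.80 × 0.20 + 0.50 × 0.50)]² / 0.30² = (1.322 + 0.539)² / 0.09 = 38.5, rounded up to 39.

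This reproduces. It concerns the 3-month comparison, before crossover, so it does not change.

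**3. How far the ITT rate could move**

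Let p be the proportion meeting the 50% threshold and f the share of those who cross over anyway. The scored ITT rate is p × (1 − f). The documents give no value for f, so 10–30% is an assumption. Using 80% and 50% after 3 months is a second assumption, since they are planning values for 3 months.

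| f | FJI rate, 0.50 × (1 − f) | C-RFA rate, 0.80 × (1 − f) | Gap, FJI only switches | Gap, both arms switch | Gap, C-RFA only switches |
|---|---|---|---|---|---|
| 0 | 50% | 80% | 30 | 30 | 30 |
| 10% | 45% | 72% | 35 | 27 | 22 |
| 20% | 40% | 64% | 40 | 24 | 14 |
| 30% | 35% | 56% | 45 | 21 | 6 |

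Gaps are in percentage points: 0.80 − 0.50(1 − f), 0.30(1 − f), and 0.80(1 − f) − 0.50. With 135 enrolled and 67 in the FJI arm, the FJI-only case involves 67 × 0.50 × 0.10 = 3.4 to 67 × 0.50 × 0.30 = 10.1 participants.

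**4. Effect on a test**

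Suppose instead that the true rate is 50% in both arms, 68 vs 67 are analysed without attrition, and only FJI successes switch. The probability of p ≤ 0.05 by Fisher's exact test, the plan's test for categorical variables, is 3.9% at f = 0, and about 7%, 18% and 38% at f = 10%, 20% and 30%. This shows how sensitive the result is under one-sided switching; it does not predict what will happen.

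**The case against.** The strongest reply is that the texts can be read as one rule. The Follow-up sentence is permissive and does not say that only failures may switch, and the Blinding paragraph refers to crossover criteria as though a single set existed. If adequate relief simply means the success criterion, the conflict disappears. That reading is plausible, but nothing in the plan states it.

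Second, scoring a change of procedure as failure is a recognised composite strategy, and it is prespecified here. This stands: the scoring rule is not an error in itself. What fails is the claim that it follows by definition from the success criterion.

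Third, the affected ITT analysis is not the main report after 3 months. This also stands and limits the weight of the point.

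Fourth, NPRS is already collected at 1, 3, 6, 12 and 24 months, so a pre-crossover score exists for those who attend. It need not be close to the decision, however: between the 12- and 24-month visits it could be about a year old.

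A reader might also infer three stronger things that the documents do not support.

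- That the treatment-benefit survival analysis is distorted. The duration rule under Group Assignments ends relief when pain returns or a repeat procedure is performed. It does not name crossover, and Data Analysis does not say how the survival analysis treats it.
- That the bias favours C-RFA. Lack of blinding makes differential requests possible, not demonstrated, and the Follow-up text's mention of crossing to active treatment explains the 3-month timing rather than participants' preferences.
- That the primary result is at risk. It is calculated before crossover opens.

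**Conclusion.** The point holds as an inconsistency between stated rules, and it should be corrected. Followed as written, the plan allows a participant with at least a 50% NPRS reduction to be counted as an ITT failure after 3 months. The 3-month primary result and the sample size are untouched. The direct effect is on the secondary long-term report; the same ambiguity also governs membership of the as-treated groups, which form the primary long-term report.

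The size and direction cannot be determined from the documents. Under the assumptions above, the 30-point gap could widen to 35–45 points or shrink to 27–21, depending on whether switching among successes occurs in the FJI arm alone or equally in both. The conclusion rests on adequate relief not having been intended as the 50% criterion, or at least on the plan not saying that it was.

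**What to change.** 1. Reconcile the two Follow-up statements, the Crossover paragraph and Data Analysis so that one crossover criterion applies and its relation to the success definition is explicit. Which clinical criterion to adopt is for the investigators; none is proposed here.
2. Record NPRS at the crossover decision, on the same measure as the primary outcome.
3. Report crossovers by arm and by whether they met the failure definition at that time.
4. Keep the ITT analysis that scores crossovers as failures, and add one sensitivity analysis that classifies each crossover by the last pre-crossover NPRS. It answers a somewhat different question, so it supplements the planned analysis rather than replacing it.

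The cost is a wording amendment, one extra NPRS score per crossover and one extra analysis. The score has to be collected prospectively, since it may not be recoverable later.

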**Power Analysis**

In the Dreyfuss et al prospective cohort study of conventional RFA for the treatment of chronic lumbar facet joint pain, which used an identical diagnostic/selective MBN block protocol (SIS guidelines), to that of the proposed study, 87% of patients experienced at least 60% reduction in pain at 10-month follow-up. For the present power analysis, we will more conservatively estimate a success rate of 80%, using 50% relief in pain at 3 months as the definition of success.

No study to date has used dual comparative MBN blocks to select patients for facet joint injection of corticosteroid. However, Carette et al. used intra-articular injection of local anesthetic only (>50% relief considered “positive) in order to select patients for a randomized controlled trial of lumbar facet joint injection of corticosteroid versus saline. In this study, a 42% success rate was observed at 3 months. For the present power analysis, we will more conservatively estimate a success rate of 50% at 3 months, as participants will be selected by dual comparative MBN blocks rather than only one intra-articular diagnostic injection.

Given that the primary analysis will be categorical in nature (comparison of the proportion of responders), with an alpha level of 0.05 and a power of 0.80, 39 participants would be needed in each group (total 78 participants) to detect a significant difference in the proportions between the two groups (80% vs. 50%) using a chi-square test. However, in order to improve the power of the study beyond the minimally acceptable standard and to account for anticipated attrition, we propose to enroll 135 patients in the trial.

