### *Statistical Analysis*

Descriptive statistics and graphical displays will be used to examine the central tendency and distribution of each outcome variable. Data will be analyzed using Stata (ver. 14.2, StataCorp LLC, College Station, TX, USA). An alpha level of 0.05 and two-tailed tests will be used for all hypothesis testing.

To illustrate the demographic, radiologic, and procedural characteristics of the study sample, means and standard deviations or medians and interquartile ranges (depending on the distribution of data) will be calculated for continuous variables, and frequencies and proportions will be calculated for categorical variables. Demographic, clinical, and radiologic differences will be compared between the groups (C-RFA vs. FJI) in order to ensure that the two groups are equal in terms of observed as well as unobserved covariates other than the treatment provided to them.

In comparing groups (C-RFA vs. FJI) with regard to categorical variables, Fisher's exact tests will be used. Proportions and 95% confidence intervals will also be calculated in order to confirm that any differences between groups are truly distinguished. A proportion ratio will be calculated as the measure of the effect size. For quantitative variables, independent *t*-tests or Wilcoxon-Mann-Whitney tests will be used to compare means or medians, respectively. An effect size of *r* will be calculated to examine the magnitude of a group difference.

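### Crossover restarts a 2-year outcome period, but no assessment is required just before the crossover procedure and no reference score is named for it

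*Combined protocol and SAP*

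**What the plan says.** - **Baseline.** Study Timeline, Baseline: "all baseline questionnaires will be completed within 8 weeks before the index study treatment procedure". No second baseline is described.
- **Crossover.** Study Protocol, Crossover: a participant without adequate relief may ask to switch at any time after the 3-month visit, and then "a new 2-year follow-up will begin for this participant who is now placed in the alternative treatment group for the long-term, as-treated outcomes analysis". Study Timeline, Follow-up also starts a new 2-year period at crossover, but says in the same paragraph that these participants stay on the regular visit schedule.
- **Reference for relief.** Group Assignments refers to "Participants who reported 50% or more relief of their usual pain (NPRS score compared to baseline"), to identify 3-month responders who may be offered a repeat procedure. The primary responder definition asks for an NPRS reduction of at least 50% at 3 months and names no reference score. Duration of relief is tied to pain before treatment, without saying which treatment.
- **Analysis.** Data Analysis plans both intention-to-treat and as-treated analyses beyond 3 months, with as-treated as the main report. In the intention-to-treat analysis a crossover counts as a failure of the assigned treatment.

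**The concern.** The plan restarts the clock and changes the treatment label at crossover, but does not reset or name the score from which change is measured. Crossover can fall between visits. Between the 12- and 24-month visits, for example, the last scheduled score may be up to about 12 months old (24 − 12, before visit windows). The text then provides no fresh NPRS, ODI, PF-CAT, Global-10 or analgesic record from just before the second procedure.

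If the analyst falls back on the index baseline, the second treatment is credited or charged with whatever change was already present. For example, baseline NPRS is 8 and pre-crossover NPRS is 5, a 37.5% reduction and so a failure. If post-crossover NPRS is 4, the participant is a responder against the index baseline (4/8 = 50%), although the second procedure lowered pain by only 20% (1/5).

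At stake are the as-treated long-term results for each treatment, including the duration of relief up to 2 years in Specific Aim 1.

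**Working it through.** **1. The plan's own figure.** Power Analysis states "39 participants would be needed in each group (total 78 participants", for "80% vs. 50%) using a chi-square test" "with an alpha level of 0.05 and a power of 0.80"; Statistical Analysis makes tests two-sided. The pooled-variance formula without continuity correction gives

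n = [1.960·√(2·0.65·0.35) + 0.842·√(0.8·0.2 + 0.5·0.5)]² / 0.30² = (1.322 + 0.539)² / 0.09 ≈ 38.5, so 39 per group.

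The stated size reproduces. It is used here only for the response rates. The plan gives no figure for the crossover analysis.

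**2. How many could cross over.** The plan says "we propose to enroll 135 patients in the trial", which at 1:1 is 67.5 per arm. Expected 3-month failures are 67.5 × 0.50 = 33.75 for FJI (these would become C-RFA episodes) and 67.5 × 0.20 = 13.5 for C-RFA (these would become FJI episodes). No crossover rate is given, so these are upper figures at the 3-month visit.

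**3. Threshold arithmetic (no distribution assumed).** Let r be the improvement from index baseline still present just before the second procedure. Reaching 50% below the index baseline then needs a further fall of 1 − 0.5/(1 − r) from current pain.

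| r | further fall needed, index baseline | fall needed, pre-crossover score |
|---|---|---|
| 20% worse | 58.3% | 50% |
| 0% | 50% | 50% |
| 10% | 44.4% | 50% |
| 20% | 37.5% | 50% |
| 30% | 28.6% | 50% |
| 40% | 16.7% | 50% |

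With baseline 7 and pre-crossover 4.2 (r = 40%), 0.7 points more makes a responder on the index baseline, against 2.1 points on a pre-crossover score.

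**4. Effect on response among crossover episodes (assumed inputs).** Simulation with 400,000 participants and whole-number scores: baseline NPRS normal with mean 7 and SD 1.3, limited to 5–10; first-treatment reduction normal with mean m and SD 20%, keeping those below 50%; second-treatment reduction normal with mean e and SD 25%. For m from 10% to 30%, mean improvement at crossover is about 9–23%.

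| m | e | responders, index baseline | responders, pre-crossover score | difference |
|---|---|---|---|---|
| 10% | 0% | 8.5% | 3.6% | +4.9 |
| 30% | 0% | 15.7% | 3.9% | +11.8 |
| 10% | 40% | 50.8% | 41.1% | +9.7 |
| 30% | 40% | 65.3% | 42.5% | +22.8 |
| −10% (worse) | 40% | 36.4% | 40.3% | −3.9 |

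Listing all whole-number score combinations shows the same dependence. If nobody is worse at crossover, 19 combinations are successes on the index baseline only and none on the pre-crossover score only. Once worsening is allowed, it is 19 each way.

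A different assumption, with leftover improvement spread evenly over 0–49%, nobody worse, and an SD of 30 points for the second response, turns a true 50% into 71% (67–78% for SDs of 40 down to 20 points).

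**5. Effect on the pooled as-treated difference.** Suppose all failures cross over and each crossover episode is added to the 67.5 first-treatment episodes of its new group. An overstatement d among crossovers shifts C-RFA by 33.75·d/101.25 = d/3 and FJI by 13.5·d/81 = d/6. The difference moves by d/6: 0.8 points at d = 5 and 3.8 at d = 23.

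Under the evenly spread assumption (SD 30), true crossover response of 50% both ways moves the rates from 70% vs 50% to 77% vs 54%, a difference of 20.0 against 23.6 points. With 80% and 50%, both rates rise (to 84% and 54%) and the difference stays at about 30 points.

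**The case against.** A reader might infer that the plan instructs the analyst to use the index baseline after crossover. It does not. The phrase comparing NPRS with baseline governs the offer of a repeat procedure, and the pre-treatment pain level in the definition of duration of relief can fairly be read as pain before the crossover procedure. This objection stands: the reference is unspecified, not wrongly specified. But even on the favourable reading, the plan does not secure the score that it would need.

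A reader might also infer that no usable score exists and that the loss is always irrecoverable. That goes too far. All follow-up measures are due at 3 months, before any crossover, and again at 6, 12 and 24 months. A crossover soon after a visit could have a score within the 8 weeks that the plan accepts for the index baseline. The gap is real for between-visit crossovers, and no visit score is designated in any case.

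A third tempting inference is that the as-treated comparison is tilted materially towards C-RFA. More crossovers into C-RFA are expected on the plan's rates, but the documents give neither pain at crossover nor crossover numbers. The sign can reverse, and the pooled difference moves little.

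Finally, a pre-crossover score is not bias-free. It is taken when the participant seeks a change, so some regression to the mean will favour the second treatment. The timeline figure is not available for this review, so the finding rests on the text alone.

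**Conclusion.** The point holds as an unsecured and unnamed reference score for the main long-term analysis, and should be corrected. If the index baseline is used, residual change from the first treatment is attributed to the second; the threshold arithmetic shows this without any distributional assumption. The size and sign in practice depend on pain at crossover, which the documents do not give.

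Under the simulation's assumed mean prior improvement of about 9–23%, response among crossover episodes is overstated by about 5–23 percentage points. Other assumptions give larger, smaller or reversed effects. With the same overstatement in both directions, the pooled as-treated difference moves by about 1–4 points even if every 3-month failure crosses over, and it can stay nearly unchanged. What is mainly exposed is each treatment's own reported long-term effectiveness, more than the contrast between them. The 3-month intention-to-treat comparison precedes crossover, and the long-term intention-to-treat analysis counts crossovers as failures, so neither is affected.

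**What to change.** - **Study Timeline and Study Protocol, Crossover:** require the existing self-report instruments (7-day and current NPRS, ODI, PF-CAT, Global-10, analgesic use) to be completed after the crossover decision and before the crossover procedure.
- **Data Analysis:** name that score as the reference for post-crossover response, MCID change and duration of relief. Report the index-baseline version as a sensitivity analysis. Show crossover episodes separately from first-treatment episodes.
- **Study Timeline, Follow-up:** reconcile staying on the regular visit schedule with starting a new 2-year period.

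The cost is one extra questionnaire set per crossover and a few sentences of text. Participants with low pre-crossover pain will have less room to respond, and some regression to the mean will remain in a score taken when the participant seeks crossover; the separate display and the sensitivity analysis let readers judge both. No treatment, eligibility or crossover rule changes, and the randomised 3-month analysis stays as it is.
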